- b For most patients, the final visit of the originating study (RHBV, RHBW, or RHBX) will coincide with Visit 1 (Week 0) of Study RHBY. However, in particular circumstances, the duration between the final visit of the originating study and Visit 1 (Week 0) of Study RHBY may be extended after consultation with the sponsor. Therefore, there is no specified visit window for Visit 1 (Week 0) of Study RHBY.
- c Patients will be assigned to Group A or Group B at Visit 5/Visit 505 (Week 24).
- d A complete physical examination (excluding pelvic, rectal examination) will be performed at baseline. All physical examinations throughout the study are to include a symptom-directed physical as well as examination of heart, lungs, abdomen, eyes, and visual examination of the skin.
- e Patients are to be resting for a minimum of 5 minutes prior to vital sign collection. Blood pressure and pulse will be measured in sitting position and will be recorded before IP dosing at all visits.
- f Weight is only captured on eCRF at Visit 1 (Week 0), Visit 10/Visit 515 (Week 64), Visit 14/Visit 519 (Week 104), or ETV. Body weight collected at other visits is used only for calculation of creatinine clearance.
- g Habits include recording of caffeine, alcohol, and tobacco consumption.
- h If patients are not eligible to enter Study RHBY at Week 52 in the originating study (e.g., due to unresolved safety concerns), then entry into Study RHBY may be delayed beyond Week 52 of the originating study. See Section 6.1.
- i Patients who have achieved a state of sustained remission (Group B) will participate in randomized withdrawal–retreatment and will be randomized to their treatment assignment at Week 24. See Section 5.1.
- j Evaluation includes both historical events as well as preexisting conditions which are assessed after baseline to determine any treatment-emergent worsening of preexisting conditions. Adverse events that initiated in the originating study (RHBV, RHBW, or RHBX) and are ongoing by the time the patient completes participation in the originating study will be considered as preexisting conditions in Study RHBY.
- k Patients need to be asked about presence of eye symptoms; if eye symptoms are present then an eye examination is required. See Section 9.4.5.

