### ***6.1.3. General Considerations for Analyses during the Extension Period Including the Double-Blind RW Period (Period 2)***

#### **6.1.3.1. RW ITT and RW Safety Populations**

For patients who are randomized in Period 2 (group B), comparisons between Combined Ixekizumab treatment group and placebo, as well as between each ixekizumab regimen (80 mg Q2W or 80 mg Q4W) and placebo, will be performed for all analyses at each scheduled visit in Period 2 including Visit 515 at Week 64.

Period 2 starts at the first injection of study treatment after randomization (at Week 24) and ends at the following study events:

- Prior to the first injection of study treatment at Week 64 (Visit 515) for not retreated patients who have completed visit at Week 64. If injection at Week 64 is missing, the next injection date after Week 64 is used;
- Prior to the first injection of retreatment for patients who have been retreated within Period 2;
- ETV prior to Week 64.

For patients who are in the RW ITT Population and have been retreated with the ixekizumab treatment regimen due to a flare or any other reasons, only data prior to the time of the retreatment will be included in the analysis for Period 2. Data after retreatment will be imputed using nonresponder imputation (NRI) method for categorical variables and mBOCF method for continuous variables.

The observed values after retreatment will be used for other specified analysis, for example, efficacy analysis for Flare Population with Retreatment.

For efficacy and health outcomes, baseline is defined as the last available value before the first dose of study treatment in Period 2 from the originating study and, in most cases, will be the value recorded at Week 0 from the originating study.

The primary analysis method for treatment comparisons of categorical binary efficacy and health outcome variables will be a logistic regression with treatment group, geographic region, and originating study as factors using PROC Logistic with Wald method. The odds ratio and 95% CIs will be reported; treatment difference and 95% CI will also be reported. In the case when logistic regression model does not produce statistical results due to sparse data, Fisher's exact test will be used. Same analysis will also be carried out at each of other scheduled visits in Period 2.

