For safety analysis for the RW Safety Population, baseline is defined as the last nonmissing assessment prior to the first injection of study treatment in Period 2.

Fisher's exact test will be used for all adverse event (AE), discontinuation, and other categorical safety data. Continuous vital sign and laboratory values will be analyzed by an ANCOVA with treatment and baseline value in the model.

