### **6.13.5. Vital Signs and Other Physical Findings**

Analyses will be conducted on vital signs and physical characteristics including systolic blood pressure (mmHg), diastolic blood pressure (mmHg), pulse (bpm), weight (kg), and BMI (kg/m^2).

Change from baseline to last observation for vital signs and physical characteristics will be summarized for patients who have both baseline and at least 1 postbaseline result for Period 2, Combined Periods 1 and 2, and Combined Periods 1, 2, and 3, respectively:

- The scheduled visits/measurements will be included. The unscheduled visits and the repeat measurements will be excluded.
- For the RW Safety Population for Period 2, the comparisons between treatment groups will be conducted using an ANCOVA with treatment groups and baseline value in the model.
- Data will be analyzed based on original scale.

For Period 2, Combined Periods 1 and 2, and Combined periods 1, 2, and 3, the observed values on vital signs and physical characteristics at each visit (starting at baseline) and change from baseline to each scheduled visit, respectively, will be displayed in box plots for patients who have both a baseline and at least 1 postbaseline result. These box plots will be used to evaluate trends over time and to assess a potential impact of outliers on central tendency summaries.

- The scheduled visits/measurements will be included. The unscheduled visits and the repeat measurements will be excluded.
- The following summary statistics will be included as a table below the box plot: number of patients with a baseline and at least 1 postbaseline result, mean, SD, minimum, Q1, median, Q3, and maximum.
- Data will be summarized based on original scale.

The number and percentage of patients with treatment-emergent or follow-up emergent high or low vital sign and weight at any time for Period 2, Combined Periods 1 and 2, Combined Periods 1, 2, and 3, and Period 4, respectively, will be summarized. The comparisons between and among treatment groups will be conducted using Fisher's exact test for the RW Safety Population for Period 2.

- [Table RHBY.6.9](#) defines the high and low baseline values as well as the limits that are specified as treatment-emergent and follow-up emergent. Note that weight does not have

an abnormal baseline; therefore, the treatment-emergent and follow-up emergent values are determined by change from baseline.

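### Weights measured in Period 2 before Week 64 are kept off the eCRF, so the planned Period 2 weight and BMI comparison loses retreated patients, mostly from the placebo arm

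*Protocol*

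**What the plan says.** **Collection.** The weight row of the Protocol Schedule of Activities (Section 2) is marked at Week 24 and at Weeks 32, 40, 48, 56 and 64. Footnote f limits what is kept: "Weight is only captured on eCRF at Visit 1 (Week 0), Visit 10/Visit 515 (Week 64), Visit 14/Visit 519 (Week 104), or ETV". It adds: "Body weight collected at other visits is used only for calculation of creatinine clearance".

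**Analysis.** SAP 6.13.5 makes no exception for this: "Analyses will be conducted on vital signs and physical characteristics including systolic blood pressure (mmHg), diastolic blood pressure (mmHg), pulse (bpm), weight (kg), and BMI". For the RW Safety Population in Period 2, change to last observation is tested: "the comparisons between treatment groups will be conducted using an ANCOVA with treatment groups and baseline value in the model". A patient needs a baseline and at least one post-baseline result to enter. Box plots by scheduled visit are planned, and also "The number and percentage of patients with treatment-emergent or follow-up emergent high or low vital sign and weight at any time for Period 2", with Fisher's exact test between arms. Table RHBY.6.9 sets the weight limit at a 7% gain or loss from baseline.

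**Period and baseline.** SAP 6.1.3.1 says of the Period 2 safety analyses that "baseline is defined as the last nonmissing assessment prior to the first injection of study treatment in Period 2". Among the events that end Period 2 it lists: "Prior to the first injection of retreatment for patients who have been retreated within Period 2". SAP 6.7 and 6.7.1 also list weight, weight category and BMI among the RW ITT characteristics summarized at Week 24.

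**The concern.** The SAP analyzes weight as if it were recorded like blood pressure. On the eCRF, the only weights that can fall inside Period 2 are those at Week 64 or at an early termination visit. A patient who flares and is retreated before Week 64 has left Period 2, as the SAP defines it, before either is taken.

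Whether a patient enters the comparison then depends on flare, which is the primary endpoint and is expected to differ strongly between arms. The test would set mainly placebo patients who did not flare against nearly all ixekizumab patients. Randomization no longer protects that comparison, and few placebo patients remain in it.

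A second effect concerns labelling. With no Week 24 weight on the eCRF, the last value before the first Period 2 injection is the Week 0 value, so 24 weeks of Period 1 change is reported as Period 2 change.

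**Working it through.** **Inputs.** Protocol 10.1 gives 200 randomized at 2:1, so about 133 ixekizumab and 67 placebo, with assumed flare rates of 10% and 70%. Period 2 lasts 40 weeks. Protocol 7.4 starts Period 2 retreatment at the next scheduled visit, and Group B visits are every 4 weeks.

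**The plan's own figure.** The documents give no figure for weight. The flare rates are used there only for the primary power, stated as over 99% with 200 patients and over 95% with about 150. Exact enumeration of Fisher's test gives more than 99.99% for 133 vs 67 and for 100 vs 50. Both statements reproduce and neither is in dispute.

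**Who is lost.** A patient who flares by Week 56 is retreated by Week 60, so the Week 64 weight lies outside Period 2. A patient who flares at Week 60 starts retreatment at Week 64 and keeps that visit's weight if it precedes the injection.

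**Lower count: constant hazard, flares by Week 56 (32 weeks into Period 2).**
- Placebo: hazard = −ln(0.30)/40 = 0.0301 per week; 1 − exp(−0.0301 × 32) = 61.8%; × 67 = 41.4 lost, 25.6 kept.
- Ixekizumab: hazard = −ln(0.90)/40 = 0.00263 per week; 1 − exp(−0.00263 × 32) = 8.1%; × 133 = 10.8 lost, 122.2 kept.

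**Upper count: every flare treated as retreated before Week 64.**
- Placebo: 0.70 × 67 = 46.9 lost, 20.1 kept.
- Ixekizumab: 0.10 × 133 = 13.3 lost, 119.7 kept.

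Flares that come earlier than a constant hazard move the result toward the upper count. Later flares reduce the loss below the lower count.

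**Precision.** The standard error of the difference, relative to full data, is √(1/n₁ + 1/n₂) after the loss divided by √(1/133 + 1/67) = 0.150.
- Upper count: √(1/119.7 + 1/20.1) = 0.241; ratio 1.61.
- Lower count: √(1/122.2 + 1/25.6) = 0.217; ratio 1.45.

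**Other flare rates (assumed).** With 50% on placebo and every flare counted, 33.5 of 67 placebo patients are lost. With ixekizumab flare between 10% and 30%, the standard error ratio is 1.30 to 1.34.

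**Baseline.** The SAP rule does not leave the baseline empty. It takes the Week 0 weight, which precedes randomization in both arms, so the ANCOVA is not biased by this alone. The change summaries do absorb Weeks 0 to 24. So do the 7% categories, because SAP 6.13.5 judges weight only by change from baseline. The Week 24 weight and BMI characteristics have no eCRF source.

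All counts ignore discontinuations. A patient who stops without retreatment keeps an early termination weight.

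**The case against.** **The baseline is valid.** A reader might infer that the comparison has no baseline, or a wrong one that biases the test. The documents do not support that. Week 0 is before randomization and is adjusted for, and Period 1 drift should be balanced across arms. What stands is the mislabelled change and the misclassified 7% outcome.

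**The weights may exist elsewhere.** Protocol Appendix 2 lists Cockcroft-Gault creatinine clearance among the sponsor-designated laboratory's tests, and Appendix 3.2.1 has central vendor data transferred to the sponsor. It would be too strong to say the Period 2 weights do not exist. But no passage says that weight itself is transferred, and footnote f restricts its use. The point is therefore limited to eCRF data.

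**The outputs do not strictly reduce to one visit.** Early termination weights are captured, and SAP 6.1.3.1 provides for data from discontinuation visits. The by-visit text is generic and also covers blood pressure and pulse. This is fair, but early termination weights do not help a patient who was retreated first.

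**Weight is a minor safety measure.** It is not an adverse event of special interest and no study objective names it. The combined-period summaries start from a Period 1 baseline, which fits capture at Weeks 0, 64 and 104. All of this stands. The SAP still specifies between-arm Period 2 tests on these data.

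**Better capture does not make the comparison clean.** This also stands. Period 2 ends at retreatment whatever the eCRF records, so last weights would come earlier in patients who flare, mostly on placebo.

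**Conclusion.** The mismatch between footnote f and SAP 6.13.5 is real. On eCRF data, the Period 2 weight and BMI comparison excludes patients because they flared and were retreated, and does so unequally by arm: about 62% to 70% of placebo against 8% to 10% of ixekizumab. That leaves about 20 to 26 placebo and 120 to 122 ixekizumab patients, with a standard error 1.45 to 1.61 times that with all patients.

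These figures rest on the planning flare rates, on a constant hazard (lower count) or every flare retreated before Week 64 (upper count), and on no discontinuations. At a 50% placebo flare rate about half of placebo is lost on the upper counting. The exact numbers depend on these assumptions, but a large, outcome-related and unequal loss does not.

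The damage is confined to weight and BMI in Period 2 and to their Week 24 summaries. A reader might extend it to the vital-sign analyses or to the trial's main conclusions. The documents do not support that: blood pressure and pulse are recorded at all visits, and the primary endpoint and its power do not use weight.

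**What to change.** 1. Amend footnote f so that the weights already measured from Week 24 onward are captured on the eCRF, or import them from the creatinine-clearance data if they are held there.
2. In SAP 6.13.5, use the Week 24 weight as the Period 2 baseline and the last value before retreatment as the last Period 2 observation. Nearly all randomized patients then become evaluable, apart from those retreated before the first post-baseline weight visit.
3. Report the number of patients with a weight and the time of the last weight by arm, because follow-up stays shorter in patients who flare. A by-visit comparison at an early visit such as Week 32 is less affected.
4. If the weights cannot be recovered, drop the Period 2 between-group weight and BMI tests. Report weight descriptively with the number recorded per arm, and state that the baseline is Week 0.

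The cost is one eCRF field at visits where weight is already taken, or one data import, plus a short SAP edit. There is no new patient procedure. The fallback needs only the SAP edit.

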3.1. Study Rationale

The clinical development plan to evaluate the efficacy and safety of ixekizumab in patients with axial spondyloarthritis (axSpA) includes three Phase 3 studies (I1F-MC-RHBV [RHBV], I1F-MC-RHBW [RHBW], and I1F-MC-RHBX [RHBX]; hereafter referred to as the originating studies). The current study (I1F-MC-RHBY [RHBY]) is an extension study and offers patients who have completed any of these originating studies an opportunity to continue ixekizumab (LY2439821) treatment for up to 2 additional years.

Ixekizumab is a humanized immunoglobulin G subclass 4 (IgG4) high-affinity monoclonal antibody (MAb) that selectively targets the cytokine interleukin-17A (IL-17A, also known as IL-17). Ixekizumab treatment is administered by subcutaneous (SC) injections. The demonstration of increased IL-17 producing Th17 lymphocyte numbers and serum IL-17 levels in radiographic axSpA (rad-axSpA) is consistent with a direct role of Th17 lymphocytes in this disease (Wendling et al. 2007; Jandus et al. 2008; Mei et al. 2011). IL-17 secreting cells have also been detected *in situ* in the bone marrow of facet joints obtained from patients with rad-axSpA (Appel et al. 2008). Compelling scientific information exists to date suggesting an important role of the IL-23/IL-17 pathway in the pathogenesis of axSpA (Baeten et al. 2010; Maksymowych 2010; Baraliakos et al. 2011; Reveille 2011; Baeten et al. 2013, 2014; Yeremenko et al. 2014).

Selectively targeting IL-17A with ixekizumab is hypothesized to provide therapeutic benefit without unduly impacting host defenses. As such, ixekizumab may offer a therapeutic option for patients with axSpA who have failed nonsteroidal anti-inflammatory drugs (NSAIDs), and for patients with axSpA who have lost response, failed to respond, or are intolerant to current marketed drugs. Ixekizumab may offer a more favorable safety profile compared to currently marketed therapies.

Axial spondyloarthritis requires long-term and often life-long treatment and data from withdrawal studies with tumor necrosis factor alpha inhibitors (TNF inhibitors) have shown that in most patients with axSpA, treatment needs to be maintained long-term in order to maintain response (Baraliakos et al. 2005, 2007; Brandt et al. 2003, 2005). In patients with early disease, the likelihood of maintaining response after treatment withdrawal may be somewhat higher (Haibel et al. 2008; Barkham et al. 2009; Haibel et al. 2010; and Sieper et al. 2014).

Inhibition of IL-17A represents a newer therapeutic class for the treatment of axSpA. Accordingly, there is clinical utility in understanding whether an alternative mechanism-of-action other than inhibition of TNF may offer durability in maintaining an achieved response following the withdrawal of treatment. During the double-blind, placebo-controlled, randomized withdrawal-retreatment period, the current study (RHBY) will evaluate what happens with patients who achieved sustained remission on ixekizumab treatment when they are discontinued from treatment, as well as how long it takes for these patients to relapse. In addition, the study will evaluate the effect of ixekizumab on structure progression in the spine approximately 2 years post-baseline of the originating Phase 3 study.

3.2. Background

Axial spondyloarthritis, a chronic inflammatory disease predominantly affecting the axial skeleton (sacroiliac joints [SIJ] and spine) (Poddubnyy 2013), is now recognized as a single disease entity, with a subset defined by the presence of radiographically (rad-axSpA) defined structural damage of the SIJ and a subset without clear structural damage defined radiographically (nonradiographic axSpA [nonrad-axSpA]). When comparing axSpA with rheumatoid arthritis (RA), it can be noted that while RA can be divided into erosive and nonerosive or seropositive and seronegative subsets, it is well accepted that it is still one disease. AxSpA, in a similar fashion, also has subsets, and can nonetheless be considered a single disease (Deodhar et al. 2014).

Radiographic axSpA, also called ankylosing spondylitis (AS), represents a disease in which there is evidence of disease features on radiographic imaging. It is a chronic inflammatory disease characterized by chronic inflammation of the axial skeleton and variable involvement of the peripheral joints (Braun and Sieper 2007). As the disease progresses, it can lead to new bone formation in the form of syndesmophytes and joint ankylosis, primarily in the axial skeleton. Patients with rad-axSpA may also have extra-articular manifestations of the disease such as enthesitis, anterior uveitis, psoriasis, and inflammatory bowel disease (IBD), as well as comorbidities of aortitis or cardiac conduction abnormalities. Compared with the general population, patients with rad-axSpA have increased rates of work disability, unemployment, and mortality (Boonen and van der Linden 2006).

According to several national and international referral programs (Rudwaleit and Sieper 2012; Poddubnyy et al. 2012), the proportion of nonrad-axSpA patients among all axSpA patients ranges from 40% to 60%.

Until recently, axSpA patients without radiographically defined sacroiliitis but with evidence of sacroiliitis from magnetic resonance imaging (MRI) imaging, or other characteristics of disease, have been less well diagnosed despite sharing a similar burden of disease and the same common features as patients with rad-axSpA, such as spinal inflammation, chronic back pain, positivity for human leukocyte antigen -B27, and extraarticular manifestations. Delays in the diagnosis of axSpA can postpone administration of suitable treatment by several years (Haibel et al. 2008; Landewé et al. 2012; Rudwaleit et al. 2009c; van der Heijde et al. 2006). The Assessment of Spondyloarthritis International Society (ASAS) criteria for axSpA (Rudwaleit et al. 2009a, 2009b) have been developed, in addition to a diagnostic algorithm (van den Berg et al. 2013), to facilitate earlier recognition of axSpA and to identify axSpA patients with and without radiographic sacroiliitis (Rudwaleit et al. 2004, 2005) using x-rays and MRI. Adoption of the ASAS criteria has the potential to lead to earlier identification of patients with axSpA (Rudwaleit et al. 2004), early in the disease course, and to result in more timely therapeutic intervention.

Axial spondyloarthritis affects up to 1.4% of the adult population worldwide (Braun and Sieper 2007; Reveille et al. 2012; Strand et al. 2013). Current standard of care for rad-axSpA includes regular exercise, physical therapy, NSAIDs, and TNF inhibitors (Braun et al. 2011; Ward et al. 2015). In addition, recently completed registration studies of secukinumab (an IL-17A

antagonist like ixekizumab) have also demonstrated efficacy in patients with rad-axSpA (Baeten et al. 2015; Braun et al. 2015). For patients with nonrad-axSpA, the current standard of care includes regular exercise, physical therapy, and NSAIDs. TNF inhibitors have also demonstrated efficacy in nonrad-axSpA; however, although they are approved in some geographies, they are not yet approved globally for this indication (Braun et al. 2011; Robinson et al. 2014; Ward et al. 2015), and approximately 40% of patients only obtain a partial response on TNF inhibitors (Sieper et al. 2012, 2013; Landewé et al. 2012; Dougados et al. 2014). Corticosteroid injections may also be of some benefit. Though NSAIDs are the first line of drug treatment for axSpA, they are not effective or well tolerated in all patients (Braun and Sieper 2009). In contrast to patients with RA, patients with axSpA do not respond well to conventional disease-modifying antirheumatic drugs (cDMARDs) including methotrexate (MTX) or systemic corticosteroids (Braun and Sieper 2009; Haibel and Specker 2009).

TNF inhibitors have demonstrated efficacy across the axSpA spectrum and may be prescribed when NSAID treatment has failed or cannot be tolerated (Braun et al. 2014) and where regulatory approval has been obtained for this population. To date, few treatment options are globally available for nonrad-axSpA (van der Heijde et al. 2006; Heiberg et al. 2008; Inman et al. 2008; Glintborg et al. 2010). While TNF inhibitors have proven to be effective treatments for axSpA, an unmet need remains, as not all patients respond well to or tolerate TNF inhibitor treatments (van der Heijde et al. 2006; Heiberg et al. 2008; Inman et al. 2008; Glintborg et al. 2010). While TNF inhibitors have demonstrated significant impact on signs and symptoms, function, and quality of life, they have not been able to demonstrate significant effect on structural progression in prospective clinical studies. The use of these biologic therapies in various diseases also is associated with safety concerns, such as opportunistic infections, demyelinating disorders, blood dyscrasias, reactivation of tuberculosis (TB), and exacerbation of congestive heart failure (Moreland 2005; Smith et al. 2009). There remains, therefore, a significant unmet need for safer, more effective treatments for patients with axSpA (Dougados and Baeten 2011).

